8.3.3. Treatment Comparisons

8.3.3.1. Primary Comparisons of Interest

The primary comparison of interest is to demonstrate that the change from baseline in 2-hour MMTT plasma C-peptide AUC at Week 52 in the albiglutide group is significantly different from the placebo group. The hypothesis will be tested at the 5% significance level using a two-sided test. The primary comparison will be conducted using the ITT population.

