8.3.5.3. Efficacy Analyses

8.3.5.3.1. Primary Efficacy Analysis

The primary efficacy endpoint is change from baseline in 2 hour MMTT plasma C-peptide AUC at Week 52. The primary comparison is between this value in the albiglutide group and the placebo group, adjusting for baseline 2 hour MMTT plasma C-peptide AUC and age.

A mixed-effects model for change from baseline in 2 hour MMTT C-peptide AUC will be used to estimate and compare the albiglutide and placebo treatment effects at Week 52. Specifically, a repeated-measures mixed-effects model will be fitted with change from baseline 2 hour MMTT plasma C-peptide AUC as a dependant variable and baseline 2 hour MMTT C-peptide AUC, age group, treatment group, visit, and treatment group-by-visit interaction as independent variables. Historical placebo information with 50% weight will be incorporated into the mixed effect model by Bayesian modelling using SAS PROC MCMC procedure. The mixed effects model will use a general (unstructured) covariance matrix as specification for the covariance among observations from the same subject.

A test of the treatment group difference at Week 52 will be provided by the comparison of the appropriate treatment group*visit least square means (Least square means).

The difference will be considered significant if the two-sided p-value for the comparison between treatments in change from baseline 2 hour MMTT C-peptide AUC is less than or equal to 0.05. The corresponding 95% confidence intervals will also be presented.

Subjects are scheduled to have on-therapy MMTTs performed at Week 16, 28, 52. Using a longitudinal repeated-measures model will provide an unbiased treatment difference estimate for the Week 52 time point, with better precision achieved by accounting for intra-subject variability than an analysis of covariance approach. In the event of missing observations at Week 52, the planned analysis and test are valid under a “missing at random (MAR)” assumption where missing data may depend on prior observations.

The above repeated mixed-effects model analysis will be repeated without placebo information from DEFEND1, and with 100% placebo information from the DEFEND 1 study as sensitivity analyses.

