Study Design	
 This is a Phase II, randomised, double-blind, parallel group, placebo-controlled, multicentre study of 52 weeks treatment duration in subjects with NOT1DM. Approximately 68 eligible subjects will be randomised in a 3:1 ratio such that 51 subjects receive albiglutide 30 mg once weekly (with blinded increase to 50 mg once weekly at Week 6 if the 30 mg dose is tolerated) added-on to insulin therapy and 17 subjects receive placebo once weekly added-on to insulin therapy. Historical data from placebo patients, aged 18-30 from the DEFEND-1 study [GlaxoSmithKline Document Number, 2011N125757_00] will be incorporated into the primary endpoint analysis, using Bayesian analysis. Blinded reduction of randomised study medication to the 30 mg once weekly dose may occur in the event of GI intolerance (i.e., nausea, vomiting or diarrhoea) after discussion between the investigator and medical monitor. During the study, subjects will perform self-monitored plasma glucose monitoring at least 4 times daily and adjust their basal and meal-time insulin requirements according to protocol-defined algorithm/guidance. A sample size of 60 evaluable subjects (45 in the albiglutide group and 15 in the placebo group) provides 90% power to detect a treatment effect in the primary endpoint of the current study in the range of 0.19 nmol/L (using data from all 53 placebo subjects aged 18-30 from the DEFEND-1 study) to 0.30 nmol/L (not using any historical data). The corresponding minimal detectable difference will be 0.12 nmol/L to 0.18 nmol/L, respectively. The total duration of a subject's participation will be approximately 72 weeks (up to 8 weeks of Screening, 52 weeks of treatment and 12 weeks of Post-treatment Follow-up).
Planned Analyses	
 No interim analysis is planned for this study. All decisions regarding final analysis, as defined in this RAP document, will be made prior to unblinding of the study data.

Overview	Key Elements of the RAP
Analysis Populations	
 The 'Intent to Treat' Population will be used to evaluate study efficacy. The 'Safety' Population will be used to evaluate study population characteristics, safety and PD/Biomarkers, and the 'PK' Population to evaluate pharmacokinetics.

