2.4. Statistical Hypotheses

For this Phase II, randomised, multicentre, double-blind, placebo controlled study, the primary objective is to evaluate the efficacy of albiglutide versus placebo on endogenous insulin secretion. The primary efficacy analysis endpoint will be change from baseline stimulated 2 hour MMTT C-peptide AUC at Week 52 following one year of treatment.

The primary endpoint analysis, incorporating historical placebo data from the DEFEND-1 study, will be performed using a Bayesian analysis and will therefore not utilise hypothesis testing.

However, in a non-Bayesian sensitivity analysis of the primary endpoint (excluding historical placebo data from the DEFEND-1 study) the treatment effect will be evaluated using the least squares means contrast relative to placebo. This contrast will be evaluated inferentially with a 2-sided t-test at the 0.05 criterion significance level.

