weakly informative prior is Normal with large variance,

w is how robust the prior is considered to be e.g. w=0 is pure weakly informative prior; w=1 is the historical prior.

The weighting of the DEFEND-1 placebo data depends on its similarity to the GLP110933 study placebo data. The mixture prior down-weights the historical data when the historical data does not agree with the GLP110933 study placebo data. The mixture prior up-weights the historical data when the historical data agrees with the GLP110933 study placebo data. The choice of w determines how quickly historical information is discounted as prior-data conflict increases. The primary analysis will use a w value of 0.5; this corresponds to the choice of 50% weighting for the primary analysis as planned in the protocol.

The model will use a general (unstructured) covariance matrix as specification for the covariance among observations from the same subject. The model will provide an unbiased treatment difference estimate for the Week 52 time point, with better precision

achieved by accounting for intra subject variability than an analysis of covariance approach. In the event of missing observations at Week 52, the planned analysis and test are valid under a “missing at random (MAR)” assumption where missing data may depend on prior observations.

This Bayesian analysis will derive the posterior distribution for the C-peptide treatment difference (Albiglutide – placebo), which will be plotted and an estimate of the treatment difference (median) and 95% (highest posterior density (HPD)) credible interval will be produced, together with the construction of the following probability statements:

- probability that the treatment difference ≥ 0.2 nmol/L (clinically relevant “good effect”)
- probability that the treatment difference is ≥ 0.1 nmol/L (clinically relevant “some effect”)
- probability that the treatment difference ≥ 0 nmol/L (“no effect”).

Sensitivity Analysis (MMRM with weighting of 0% and 100% DEFEND-1 Placebo Data) – All On-Study Data

Sensitivity analyses will be performed for the primary Bayesian analysis using PROC MCMC, repeating the analysis described above but using the following values for w:

- w=0; corresponding to without historical placebo data.
- w=1; corresponding to 100% historical placebo data.

Non-Bayesian Sensitivity Analysis (MMRM) – All On-Study Data

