As a further sensitivity analysis, a non-Bayesian repeated measures mixed effect model using PROC MIXED will be fitted, using all valid efficacy assessments during the study period. This model will not include any historical placebo data from the DEFEND-1 study. This analysis will be performed using the MMRM approach, as described for the secondary endpoints in Section 8.1.2 (change from baseline in stimulated (from MMTT) 2 hour plasma C-Peptide AUC at Week 16, 28 and 64). For this analysis only:

A test of the treatment group difference at Week 52 will be provided by the comparison of the appropriate treatment group-by-visit least square means (LS means).

The difference will be considered significant if the two sided p-value for the comparison between treatments in change from baseline 2 hour MMTT C-peptide AUC is less than or equal to 0.05. The corresponding 95% confidence intervals will also be presented.

Additional sensitivity analyses are described in Section 7.1.2.

The details regarding MMTT assessments are provided in Section 11.11.

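### The SAP takes the protocol's significance rule off the primary Bayesian analysis and puts no success rule in its place, so the 0.19 nmol/L end of the 90% power range has no decision rule behind it

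*SAP*

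**What the plan says.** **Protocol.** Section 8.3.3.1 states "The hypothesis will be tested at the 5% significance level using a two-sided test", and section 8.1 says the same. Section 8.3.5.3.1 describes the repeated-measures model with DEFEND-1 placebo information at 50% weight and then gives its criterion: "The difference will be considered significant if the two-sided p-value for the comparison between treatments" is at most 0.05. The rule therefore belongs to the borrowing analysis.

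**SAP, primary analysis.** Section 2.4 (and the Hypothesis row of the synopsis) says the primary analysis "will be performed using a Bayesian analysis and will therefore not utilise hypothesis testing". Sections 7.1.1.1 and 7.1.2 list its outputs: a posterior median, a 95% highest posterior density interval, a plot, and three probabilities. The first is the "probability that the treatment difference ≥ 0.2 nmol/L"; the others use 0.1 and 0. No cut-off or interval rule is attached to any of them.

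**SAP, where the test went.** For the non-Bayesian sensitivity model without DEFEND-1 data, section 2.4 says "This contrast will be evaluated inferentially with a 2-sided t-test at the 0.05 criterion significance level", and section 7.1.1.1 repeats the protocol's sentence: "The difference will be considered significant if the two sided p-value for the comparison between treatments" is at most 0.05.

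**SAP, power and change log.** The synopsis still says that 60 evaluable subjects (45 and 15) "provides 90% power to detect a treatment effect in the primary endpoint of the current study", from 0.19 nmol/L with all 53 historical subjects to 0.30 nmol/L with none. Table 1 in section 2.1, which is meant to hold the changes from the protocol analysis, records the new prior and the model terms but not the removal of the significance criterion. Section 7.1.2, on missing data, still refers to a primary hypothesis test.

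**The concern.** Power is a property of a decision rule. Once the rule is removed from the borrowing analysis, a power figure that assumes borrowing no longer describes anything that analysis will do. The 3:1 allocation, with only 15 evaluable placebo subjects, was justified in protocol 3.2 by the historical data. Yet the one significance statement that will be made on the primary endpoint comes from the model that discards those data.

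The practical risk is in interpretation. With three probabilities and no threshold, which of them counts, and how high it must be, can be settled after the results are seen. The SAP synopsis says all decisions on the final analysis are made before unblinding; this one is not made.

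**Working it through.** **Inputs.** SD 0.31 nmol/L and two-sided 0.05 (protocol 8.2.1); 45 and 15 evaluable (protocol 8.2.1, SAP synopsis); 53 historical placebo subjects; historical prior Normal(-0.269, SE 0.043), weakly informative prior with SE 1000, w = 0.5 (SAP 7.1.2).

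**1. Reproducing the plan's figures.** SE = SD × √(1/45 + 1/nP), with nP = 15 (no borrowing) or 15 + 53 = 68 (full borrowing). Power = Φ(d/SE − 1.96).

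- No borrowing: SE = 0.31 × √(1/45 + 1/15) = 0.0924. At 0.30: Φ(3.246 − 1.96) = 90.1% (noncentral t 89.1%).
- Full borrowing: SE = 0.31 × √(1/45 + 1/68) = 0.0596. At 0.19: Φ(3.189 − 1.96) = 89.1% (noncentral t 88.5%).
- Minimal detectable differences: 1.96 × 0.0924 = 0.181 and 1.96 × 0.0596 = 0.117, against the stated 0.18 and 0.12.

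The stated range is therefore the power of a two-sided 0.05 two-sample test with a fixed number of borrowed subjects. Protocol Table 5 is headed one-sided, but its zero-weight column (58%, 66%, 90%) matches the two-sided calculation (58.1%, 66.3%, 90.1%); one-sided would give 69.8%, 76.9% and 94.5%.

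**2. The surviving test at the borrowing effect size.** No borrowing, d = 0.19: Φ(2.056 − 1.96) = 53.8% (noncentral t 52.5%). With the SAP's SD of 0.314: 52.8% (51.4%).

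**3. What an illustrative rule would do.** Take success as P(albiglutide − placebo > 0) ≥ 0.975, assuming known SD 0.31, 45 versus 15, and the SAP's mixture prior with w = 0.5. In simulation the historical component kept an average posterior weight above 0.99 for true placebo means from −0.40 to −0.10, so a closed form using that component alone is a fair check:

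- Precisions: prior 1/0.043² = 540.8; current placebo 15/0.31² = 156.1; total 696.9. History's share is 0.776, current placebo's 0.224.
- Posterior SD of the difference = √(0.31²/45 + 1/696.9) = 0.0598; threshold on the estimate = 1.96 × 0.0598 = 0.117.
- Sampling SD of the estimate = √(0.31²/45 + 0.224² × 0.31²/15) = 0.0496.
- Bias = 0.776 × (true placebo mean + 0.269).

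| True placebo mean | Quantity | Closed form | Simulated |
|---|---|---|---|
| −0.269 | Power at 0.19 | Φ((0.19 − 0.117)/0.0496) = 93% | 93% |
| −0.269 | False positive | Φ(−0.117/0.0496) = 0.9% | about 1% |
| −0.20 | False positive | bias 0.0535; Φ((0.0535 − 0.117)/0.0496) = 10% | 10% |
| −0.10 | False positive | bias 0.131; Φ((0.131 − 0.117)/0.0496) = 61% | 59% |

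The nominal one-sided rate for a 0.975 rule is 2.5%. The actual rate depends on where the current placebo mean lies relative to DEFEND-1.

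**The case against.** The other side has several fair points.

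- **The power sentence is a range, and it discloses the loss.** A reader might infer that the SAP claims 90% where the truth is 54%. It does not: the synopsis ties 0.19 to full use of the historical data and gives 0.30 for none, where the surviving test does have 90%. Protocol Table 5 already shows 58% at 0.20 with zero weight. This stands.
- **Estimation without a test is legitimate in a small Phase II study, and the SAP says openly that this is its choice.** The 95% credible interval shows whether zero is excluded, and the SAP labels 0.2 and 0.1 nmol/L as clinically relevant effects. This also stands: the lack of a p-value is not itself a fault. But the SAP does not say that excluding zero, or any probability level, is how the result will be read.
- **The stakes have fallen.** Table 1 says the company is not developing albiglutide for type 1 diabetes, and section 11.6.1 records poor enrolment. The protocol's aim of determining next steps carries less weight than it did. That lowers the priority, but does not explain an unlogged change or a power figure without a rule.
- **A 0.975 rule would not bring back the protocol's test.** A reader might infer that P(difference > 0) ≥ 0.975 is the two-sided 0.05 rule under another name. Step 3 of the working shows it is not under this prior.

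**Conclusion.** The concern holds in a limited form. The SAP removed the protocol's two-sided 0.05 criterion from the primary borrowing analysis, did not log that in Table 1, and set no rule for judging the posterior. Of the stated 90% power range, the 0.30 nmol/L end still describes a test in the SAP. The 0.19 nmol/L end does not: the analysis with all 53 subjects survives as the w = 1 sensitivity run, but without a decision rule. The only test remaining for the Week 52 primary endpoint has about 53-54% power at 0.19.

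That figure assumes SD 0.31, 45 versus 15 evaluable subjects and no gain from baseline adjustment, the simplification the protocol itself made. The rule-based figures (93% power at 0.19, false positives about 1% to 59%) also assume a known SD and the illustrative 0.975 rule, and are given only to show why a rule needs its own operating characteristics. The documents do not support reading this as a miscalculation in the synopsis, or as showing that a Bayesian primary analysis is improper.

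**What to change.** Before unblinding:

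1. In SAP 2.4 and 7.1.1.1, state the rule by which the primary posterior will be judged, for example P(albiglutide − placebo > 0) ≥ 0.975 or the 95% credible interval excluding 0. Do not describe it as restoring a 5% error rate. Report its simulated power and false-positive rate under the actual w = 0.5 mixture prior over a range of true placebo means, including values away from −0.269.
2. In the synopsis, tie the power statement to that rule, or label 0.19 to 0.30 nmol/L as the protocol's design-stage two-sided 0.05 calculation. Either way, say that the retained no-borrowing test reaches 90% only at 0.30.
3. Add the dropped criterion to Table 1, and reconcile the reference to a primary hypothesis test in section 7.1.2 with section 2.4.

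The cost is SAP wording and a short simulation. The posterior quantities are already planned, and no data collection changes.

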3. PLANNED ANALYSES

3.1. Interim Analyses

No interim analysis is planned for this study.

3.2. Final Analyses

The final planned primary analyses will be performed after the completion of the following sequential steps:

1. All subjects have completed the study as defined in the protocol.
2. All required database cleaning activities have been completed and final database release and database freeze has been declared by Data Management.
3. All criteria for unblinding the randomisation codes have been met.
4. GSK have authorised unblinding of randomisation codes by PPD
5. Randomisation codes have been distributed within PPD according to PPD procedures

4. ANALYSIS POPULATIONS

Population	Definition / Criteria	Analyses Evaluated
Intent-To-Treat (ITT)	
 • Comprised of all randomised subjects who receive at least 1 dose of study medication and who have at least 1 post-baseline assessment of the primary endpoint. • This population will be based on the treatment to which the subject was randomised. • Any subject who is assigned a randomisation number by the PPD IRT system will be considered to have been randomised. 	
 • Efficacy • Exploratory endpoints, including QoL
Safety	
 • Comprised of all subjects who receive at least one dose of study treatment. • This population will be based on the treatment the subject actually received (see Section 4.2). 	
 • Study Population • Safety/tolerability • PD/Biomarkers
Pharmacokinetic (PK)	
 • Subjects in the 'Safety' population for whom a pharmacokinetic sample was obtained and analysed. • Only subjects who received albiglutide will be included in the PK population. 	
 • PK

NOTES :

- Refer to [Appendix 13](#): List of Data Displays which details the population to be used for each displays being generated.

DEFEND-1 Study

Subjects from the DEFEND-1 study [GlaxoSmithKline Document Number, [2011N125757_00](#)] to be included in the Bayesian modelling for the primary analysis will be selected as follows:

- Subjects who were included in the ITT Population as defined in the DEFEND-1 RAP and study report.
- Subjects who were aged 18-30 years (inclusive). Note: Age at dosing will be used to select subjects (calculated as variable AGE in DEFEND-1 dataset).
- Subjects with non-missing values for the Baseline and Week 52 stimulated (MMTT) 2 hour plasma C-peptide AUC. LOCF values at Week 52 will be included for the DEFEND-1 study.

This selection gives the historical data from 53 placebo subjects aged 18-30 years to be included in the Bayesian analysis, as specified in the protocol for GLP110933 (stimulated 2-hour MMTT C-peptide AUC change from baseline at Week 52, mean and SD). This was based on LOCF data from DEFEND-1. The LOCF method will not be used in study GLP110933, the analysis is a repeated measures analysis. Whilst the method of handling of missing data within this analysis model is different, it was decided to use the data from DEFEND-1 as specified in the protocol (including LOCF observations), as changing to use only non-missing observed cases from DEFEND-1 would not address missing data at all.

Note: the ITT Population in DEFEND-1 was defined as all subjects who were randomised and received any part of at least 1 infusion of study drug. C-peptide AUC was calculated if there was at least one pre-MMTT sample and at least two post-MMTT samples. The population flags and derived variables from the DEFEND-1 data will be used to select the relevant subjects for inclusion as historical placebo data for the primary efficacy analysis.

Enrolled Population

For disclosure purposes, the enrolled population includes all subjects who passed screening. That is, those subjects randomised plus any subjects who passed screening but did not get assigned a treatment, e.g. a subject passed screening but withdrew consent prior to randomisation or the subject passed screening but was a run-in failure. In this study, there are no subjects who were classed as passing screening other than those who were randomised. Therefore, the enrolled population will be the same as the randomised population. The terminology 'randomised population' will be used in summary tables for simplicity.

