2.2. Study Objective(s) and Endpoint(s)

Objectives	Endpoints
Primary Objectives	Primary Endpoints

 Determine the effect of albiglutide therapy versus placebo on endogenous insulin secretion over 52 weeks when added to standard of care in subjects with new onset type 1 diabetes mellitus (NOT1DM) 	
 Primary Endpoint: Mean change from baseline in stimulated (from mixed meal tolerance test [MMTT]) 2 hour plasma C-peptide area under the curve (AUC) at Week 52 Secondary Endpoints linked to primary objective: Mean change from baseline in stimulated (from MMTT) 2 hour plasma C-peptide AUC at Week 16, 28 and Week 64 Maximum stimulated plasma C-peptide: the highest value at any time point during the 2 hour MMTT after the subject has ingested the mixed meal at Baseline, Week 16, Week 28, Week 52 and Week 64
Secondary Objectives	Secondary Endpoints

 To assess the effect of albiglutide versus placebo on plasma glucagon concentration during a MMTT Determine the percentage of subjects meeting the definition of a responder (defined as having HbA1c ≤ 7.0% and mean daily insulin use < 0.5 units/kg/day) and the percentage of subjects achieving partial remission status (i.e., defined as subjects with Insulin Dose Adjusted A1c (IDAA1c) ≤ 9.0) To assess glycaemic control in both treatment groups as measured by HbA1c Determine differences in total daily insulin dose between treatment groups 	
 Mean change from baseline in plasma glucagon AUC (from MMTT) at Week 16, 28, 52 and Week 64 Percent of responders (defined as subjects with HbA1c ≤ 7.0% and insulin dose < 0.5 units/kg/day) at Weeks 4, 8, 16, 28, 40, 52 and 64 Percent of subjects achieving insulin dose-adjusted haemoglobin A1c (IDAA1C) ≤ 9.0 at Weeks 4, 8, 16, 28, 40, 52 and 64 Change from Baseline in HbA1c at Week 52 and HbA1c over time (i.e., at Weeks 4, 8, 16, 28, 40, 52 and 64) Change from baseline in mean daily insulin use over the 3 days preceding the visit at Weeks 4, 8, 16, 28, 40, 52 and 64. The mean daily insulin use value will be calculated, in units/kg/day, as the sum of average

Objectives	Endpoints
	prandial insulin doses and average of basal insulin doses for each subject recorded daily for the 3 days prior to the specified visits, divided by the subject's body weight in kg

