
 Determine any differences in significant hypoglycaemia (i.e., events with plasma glucose ≤ 3.9 mmol/L and/or requiring third party intervention) between treatment groups 	
 Number of events of hypoglycaemia with confirmed self plasma glucose monitoring ≤ 3.9 mmol/L and/or requiring third party intervention (i.e., severe, documented symptomatic and asymptomatic hypoglycaemic events) occurring $>$Week 24 and \leqWeek 52

 Compare glycaemic variability between treatment groups, as measured by 72-hour continuous glucose monitoring (CGM) and 7 point glucose profile 	
 Time spent with a plasma glucose ≤ 3.9 mmol/L, between >3.9 and 10.0 mmol/L, and >10.0 mmol/L, respectively as performed by 72-hour CGM at Baseline, Week 28 and Week 52 Number and magnitude of hypoglycaemic (≤ 3.9 mmol/L) and hyperglycaemic excursions (>10.0 mmol/L) from the 7 point glucose profile at Baseline, Week 28 and Week 52

 Determine the effect of albiglutide on body weight 	
 Change from Baseline in body weight (kg) at Week 52 and Weight over time (i.e., at Weeks 2, 4, 6, 8, 16, 28, 40, 52 and 64)

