7. PRIMARY STATISTICAL ANALYSES

7.1. Efficacy Analyses

Efficacy Analyses will be based on the ITT population and all valid efficacy assessments during the study period.

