8. SECONDARY STATISTICAL ANALYSES

8.1. Efficacy Analyses

8.1.1. Overview of Planned Efficacy Analyses

The secondary efficacy analyses will be based on the “Intent-To-Treat” population, unless otherwise specified.

Table 5 provides an overview of the planned efficacy analyses, with further details of data displays being presented in [Appendix 13: List of Data Displays](#).

Table 5 Overview of Planned Efficacy Analyses

Secondary Efficacy Endpoints	Absolute						Change from Baseline					
	Stats Analysis			Summary		Individual	Stats Analysis			Summary		Individual
	T	F	L	T	F	F	T	F	L	T	F	F
Mixed Meal Tolerance Test (Baseline, Week 16, 28, 52, 64)												
Stimulated (from MMTT) 2 hour plasma C-peptide AUC ^[3]				Y ^[1]	Y		Y	Y		Y ^[1]	Y	
Plasma Glucagon AUC (from MMTT)				Y ^[1]	Y		Y	Y ^[4]		Y ^[1]		Y
Maximum plasma C-peptide during 2hr MMTT				Y ^[1]	Y		Y	Y ^[4]		Y ^[1]		Y
Percent of Responders (Baseline, Week 4, 8, 16, 28, 40, 52 and 64)												
HbA1c ≤7.0 and insulin dose<0.5 units/kg/day	Y ^[4]			Y	Y		Y					
IDAA1C ≤9	Y ^[4]			Y	Y		Y					
Glucose Control (Baseline, Week 4, 8, 16, 28, 40, 52 and 64)												
HbA1c				Y ^[1]	Y		Y	Y ^[4]		Y ^[1]		Y
Mean daily insulin dose				Y ^[1]	Y		Y	Y ^[4]		Y ^[1]		Y
Subject-Reported Hypoglycaemic Events												
Number of hypoglycaemias with confirmed plasma glucose monitoring ≤3.9 mmol/L and/or requiring third party intervention occurring >Week 24 and ≤Week 52				Y ^[2]			Y					

Secondary Efficacy Endpoints	Absolute							Change from Baseline						
	Stats Analysis			Summary		Individual		Stats Analysis			Summary		Individual	
	T	F	L	T	F	F	L	T	F	L	T	F	F	L
7-Point Glucose Profile														
Glucose levels at each of the 7 specified time-points of the 7-point glucose profile at Baseline, Week 28 and Week 52				Y										
Number of hypoglycaemic excursions (≤ 3.9 mmol/L) from 7-point glucose profile				Y										
Proportion of subjects with hypoglycaemic excursions from 7-point glucose profile				Y										
Greatest magnitude of hypoglycaemic excursion from 7-point glucose profile				Y										
Number of hyperglycaemic excursions (>10 mmol/L) from 7-point glucose profile				Y										
Proportion of subjects with hyperglycaemic excursions from 7-point glucose profile				Y										
Greatest magnitude of hyperglycaemic excursion from 7-point glucose profile				Y										
Listing of data from 7-point glucose profile								Y						
72-hr CGM (Baseline, Week 28, 52)														

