8.1.1.1. Supplementary Information for Subject-Reported Hypoglycaemic Events

Subject-reported hypoglycaemic events (see Section 11.5.3 and Section 11.5.4) will be used for this endpoint. This endpoint will determine any differences in significant hypoglycaemia (i.e., events with plasma glucose ≤ 3.9 mmol/L and/or requiring third party intervention); that is severe, documented symptomatic and asymptomatic hypoglycaemic events as defined by ADA category.

Incidence of severe hypoglycaemia, documented symptomatic hypoglycaemia, and asymptomatic hypoglycaemia will be tabulated by treatment group. Incidence is defined as the numbers of subject-reported hypoglycaemic events per subject, and total percentages of subjects affected. The summary table will present the average number of events per subject (i.e. the number of subject reported hypoglycaemic events divided by the number of subjects), incidence (percentages of subjects affected) and the number of events occurring by treatment group. The summary will be produced for the time period from Baseline to Week 24, and from > Week 24 to \leq Week 52.

Further exploratory analysis may be done, depending on the amount of missing data.

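### The ITT set requires a post-baseline MMTT, first due at Week 16, so subjects who leave the study earlier lose their collected HbA1c, weight and insulin-use data from the secondary models

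*SAP*

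**What the plan says.** Protocol 8.3.1 and SAP 4 define ITT in the same way: randomised, at least one dose, and subjects "who have at least 1 post-baseline assessment of the primary endpoint". The primary endpoint is C-peptide AUC from the MMTT. Protocol 8.3.5.3.1 gives the on-treatment schedule: "Subjects are scheduled to have on-therapy MMTTs performed at Week 16, 28, 52". A further MMTT follows at Week 64. The Time and Events table shows none at Weeks 2 to 8 and none at the early withdrawal visit.

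ITT governs all efficacy work. SAP 7.1: "Efficacy Analyses will be based on the ITT population and all valid efficacy assessments during the study period". SAP 8.1.1: "The secondary efficacy analyses will be based on the" ITT population unless otherwise specified. Appendix 13 lists ITT against every efficacy table, figure and efficacy listing.

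Several secondary endpoints have values before Week 16 (SAP 2.2):
- "HbA1c over time (i.e., at Weeks 4, 8, 16, 28, 40, 52 and 64"
- "Weight over time (i.e., at Weeks 2, 4, 6, 8, 16, 28, 40, 52 and 64"
- "mean daily insulin use over the 3 days preceding the visit at Weeks 4, 8, 16, 28, 40, 52 and 64"

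For efficacy hypoglycaemia, SAP 8.1.1.1 adds an early period: "The summary will be produced for the time period from Baseline to Week 24". SAP 8.1.2 puts every scheduled post-baseline visit into the secondary MMRMs, although HbA1c, insulin use and weight are tested only at Weeks 28 and 52.

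**The concern.** Eligibility for every efficacy endpoint depends on a post-randomisation measurement of one of them. For MMTT endpoints this costs nothing. For endpoints measured earlier, it removes observations that the models are specified to use.

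This weakens the plan's own missing-data argument. SAP 11.6.2.2 defends the MMRMs under missing at random, where missingness may depend on what was observed beforehand. For someone who leaves at, say, Week 10, those prior observations are the Week 4 and 8 HbA1c and insulin values and the Week 2 to 8 weights, and the ITT rule deletes them. The Safety set does not recover them: SAP 8.2.3.1 leaves weight to efficacy, and no safety table covers post-baseline HbA1c or insulin use.

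Other parts of the SAP point the other way. Section 11.2.1 maps early-withdrawal HbA1c to a missing scheduled visit when it falls in the window. Section 11.6.1 would include available data from withdrawn subjects unless otherwise specified, and Appendix 13 does specify otherwise. Section 4 describes the DEFEND-1 ITT set as randomised and dosed, with no post-baseline condition.

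**Working it through.** **1. Reproduce the plan's sample size.** Inputs (Protocol 8.2.1): 60 evaluable, 10% drop-out, 3:1 allocation.
60 / (1 − 0.10) = 66.7, so 67; the next multiple of 4 is 68, that is 51 + 17. This agrees with the plan.

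**2. How many could be excluded.** The documents give the 10% but not its timing, so the share falling before Week 16 is assumed. Expected number = N × 0.10 × share.

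| Assumed share of drop-out before Week 16 | Rate | Of 68 | Of 51 albiglutide | Of 17 placebo |
|---|---|---|---|---|
| 16/52 (even loss) | 3.1% | 2.1 | 1.6 | 0.5 |
| 1/2 | 5.0% | 3.4 | 2.6 | 0.9 |
| all | 10.0% | 6.8 | 5.1 | 1.7 |

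The arm columns assume equal rates in both arms.

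**3. Which analyses lose data.** Set the collection schedule against the ITT condition for a subject who leaves before Week 16.

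| Analysis | Post-baseline data before Week 16 | Effect of the ITT rule |
|---|---|---|
| C-peptide AUC (including primary), maximum C-peptide, glucagon AUC | none | nothing to lose |
| CGM, 7-point profile | none (Weeks 28 and 52 only) | nothing to lose |
| HbA1c MMRM | Weeks 4, 8 | lost |
| Insulin-use MMRM | Weeks 4, 8 | lost |
| Weight MMRM | Weeks 2, 4, 6, 8 | lost |
| Responder and remission summaries (Tables 2.12, 2.14) | Weeks 4, 8 | lost at those visits |
| Responder and remission tests | tested at Weeks 28 and 52, no planned imputation | unaffected |
| Hypoglycaemia, Baseline to Week 24 (Table 2.21) | diary events | lost from efficacy, kept in Safety tables |
| Hypoglycaemia, after Week 24 to Week 52 | outside the period | unaffected |

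**4. What the lost values are worth in an MMRM.** This is an illustration with assumed inputs, because the documents give none. Week 8 and Week 52 values are standard normal with correlation 0.3, 0.5 or 0.7. The chance of leaving follows a logistic model in the Week 8 value with slope 1.5 per SD. The fraction of an arm leaving is 3% (even loss), 10% (all loss before Week 16) or 14% (all 7 leavers on albiglutide: 7/51 = 13.7%).

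| Fraction leaving | Size of shift in that arm's Week 52 mean, leavers dropped (correlation 0.3 to 0.7) | Shift with their Week 8 value kept |
|---|---|---|
| 3% | 0.012 to 0.029 SD | at most 0.002 SD |
| 10% | 0.033 to 0.084 SD | at most 0.004 SD |
| 14% | 0.049 to 0.113 SD | at most 0.002 SD |

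Under these assumptions the shift is about 0.01 to 0.11 SD, and keeping the early values removes it.

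**The case against.** The strongest reply is that the plan already limits the damage.

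- **Stopping drug is not leaving the study.** Protocol 4.4 asks subjects who stop study drug to keep attending the MMTT visits through Week 64, and one valid MMTT puts them in ITT. A reader might infer that everyone who stops treatment before Week 16 is excluded; the documents do not support that.
- **Void tests are a remote route.** An out-of-range finger-stick glucose means the MMTT must be rescheduled (Protocol 6.3.2.1), and a subject would need to have no valid test at all four post-baseline MMTT visits. The SAP does leave open whether an attended but void test meets the ITT condition.
- **Hypoglycaemia is not lost to the report.** Diary events are summarised on the Safety population (SAP 8.2.1.7.3).
- **The rule is open.** Both documents state it, and exclusions from each population are reported with reasons (SAP 6.1.1).
- **Widening ITT is not automatically neutral for the primary analysis.** SAP 7.1.2 centres baseline and age on overall means and places a fixed historical prior, Normal(−0.269, SE 0.043), on the Week 52 placebo parameter. If the means were recalculated on a wider set, the covariate point at which the prior applies would move.

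All of this stands, and it narrows the point. It does not answer the loss of early HbA1c, weight and insulin values for study leavers. Transparency about the exclusion does not restore the data.

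**Conclusion.** The point holds for subjects who leave the study before any valid MMTT. They are removed from three secondary MMRMs, from the Week 4 and 8 responder and remission summaries, and from one early hypoglycaemia summary. The expected number is about 2 to 7 of 68, depending wholly on when the assumed 10% drop-out occurs. This is a minor, easily repaired weakness in secondary analyses.

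Two stronger readings are tempting. The first is that the primary result is biased by the ITT rule; it is not, because an excluded subject has no value of the dependent variable. The second is that the loss falls mainly on albiglutide, around treatment start or the Week 6 increase. Gastrointestinal intolerance makes that plausible, but the documents give neither timing nor an arm split, so it remains an assumption. The SD shifts above are likewise illustrations and not estimates for this trial.

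The planned Week 28 and 52 responder tests are unaffected, but the possible post-hoc version is not. It would count safety withdrawals as not meeting target (SAP 11.6.2.2), and while it stays on ITT it could not count those who leave before a valid MMTT.

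**What to change.** - In SAP 4, define ITT as all randomised subjects who received at least one dose, analysed as randomised. Record the change from Protocol 8.3.1 in SAP Table 1 before unblinding.
- State that each model uses subjects with a baseline and at least one post-baseline value of its own endpoint.
- In SAP 7.1.2, state that baseline and age are centred on subjects with a post-baseline MMTT. The primary estimate then does not change.
- Note that the median-age split for the responder and remission tests (SAP 8.1.2 and 11.8.1) is taken over ITT and may shift slightly.

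The cost is a few lines of text and no new data collection.
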